7.4 Subject Withdrawal Criteria

Subjects have the right to discontinue treatment and/or withdraw from the study at any time without prejudice. The investigator may discontinue any subject at any time for any reason.

7.5 Protocol Deviations

This study will be conducted as described in this protocol, except for an emergency situation in which the protection, safety, and wellbeing of the subject requires immediate intervention that

Collaborative Research Study, Version 4: 06/29/21
To Treat HRS-AKI Patients with Continuous Terlipressin Infusion

deviates from the protocol, based on the judgment of the investigator (or a responsible, appropriately trained professional designated by the investigator). In the event of a significant deviation from the protocol due to an emergency, accident, or error, the investigator or designee must contact the sponsor, or their agent, at the earliest possible time by telephone. This will allow an early joint decision regarding the subject's continuation in the study. The investigator and the sponsor will document this decision. The Institutional Review Board (IRB) will be informed of all protocol deviations by the investigator in accordance with the IRB established procedure. No deviations from the protocol of any type will be made without complying with all the IRB established procedures. Significant deviations from the protocol may not allow that patient's clinical data to be included in the Intent-To-Treat Analysis.

[figure not shown]
8 Terlipressin

Terlipressin will be supplied in single-use, sterile 6-mL vials containing 1 mg of lyophilized terlipressin acetate (equivalent to 0.85 mg terlipressin free base) with 10 mg mannitol as a bulking agent/stabilizer.

The lot numbers will be documented in the trial master file.

Figure 1: Terlipressin for Injection

Structure:

Molecular Formula: C₅₂ H₇₄ N₁₆ O₁₅ S₂

Molecular Weight: 1227.4 Daltons

Appearance: Homogenous lyophilized white to off-white solid

Solubility: Clear, colorless solution in saline

Collaborative Research Study, Version 4: 06/29/21
To Treat HRS-AKI Patients with Continuous Terlipressin Infusion

Vials: Colorless glass vials containing 11 mg of a white to off-white solid, 1 mg active ingredient and 10 mg mannitol.

The active ingredient, N-[N-(N-glycylglycyl) glycyl]-8-L-lysinevasopressin, is a synthetically manufactured hormonogen of 8-lysine vasopressin, composed of 12 amino acids and having the characteristic ring structure of a cyclic nonapeptide with a disulfide bridge between the 4th and the 9th amino acid. Three glycyl-amino acids are substituted at position 1 (cysteine) of 8-lysine-vasopressin. By this N-terminal extension of 8-lysine-vasopressin the metabolic degradation rate of the active ingredient is significantly reduced, because the glycyl molecules inhibit rapid N-terminal enzymatic degradation.

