7.2 Number of Subjects to be Studied

Prospective Terlipressin Group - approximately 50 Terlipressin treated subjects. Retrospective Control Group - approximately 15-25 subjects per clinical site that were treated for HRS-AKI according to center's standard-of-care (Midodrine/Octreotide (M&O), albumin, or other vasopressor) that would have met the inclusion/exclusion criteria below as well as having critical clinical data points to enable a comparison of the Prospective and Retrospective groups. Retrospective cases collected from each site should include eligible patients starting from prior to site IRB approval for this protocol and going back to January 2015. Subjects enrolled in a blinded clinical trial in this time period are excluded.

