8.4 Administration

Subjects in the Prospective Terlipressin Group:

Single-use, sterile 6-mL vials containing 1 mg of lyophilized terlipressin acetate (equivalent to 0.85 mg terlipressin free base) with 10 mg mannitol as a bulking agent/stabilizer.

- For initial bolus dose of 0.5mg, the vial will be reconstituted with 5 mL of sterile 0.9% sodium chloride solution and given over 1-minute push.
- Continued dosing will be by 2mg infusion per day for Days 1, and 2. For continuous infusion, the dose of terlipressin is to be dissolved in 0.9% sodium chloride solution and infused with a pump.
- If on Day 3 the SCr is not 30% lower from the baseline value, increase infusion dose to 4 mg per day.
- If on Day 5 the SCr is not 50% lower from the baseline value, increase infusion dose to 6-8 mg per day, per PI discretion. Dosing can be increased by more than 1 mg increment at Day 5 or beyond, up to a maximum of 8 mg/day.
- If the subject has infusion stopped for \geq 4 hours, a 0.5 mg bolus should be given prior to restarting infusion.
- The drug should not be used in subjects with severe coronary artery disease or in the setting of circulatory overload, pulmonary edema, or bronchospasm as determined by the Investigator. If drug therapy has been initiated, Investigator can also decide not to increase the dose, based on the patient's status with regard to the above, based on individual subject condition.

- If dosing is interrupted due to an adverse event, terlipressin may be re-started, at the discretion of the investigator, at the same or lower dose as per protocol. Terlipressin will not be restarted if dosing was interrupted due to cardiac ischemia or mesenteric ischemia.

Subjects in the Retrospective Control Group:

The dose and method of administration for Midodrine/Octreotide (M&O), albumin, or other vasopressor will be recorded as noted in the patient's medical record. To be included as a completed subject in this study, patients must have been treated for at least 48 hours with albumin infusions beyond volume resuscitation and diuretic withdrawal. Vasopressors also need to be used for a minimum of 48 hours.

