15.1 Primary Analysis

The primary analysis will utilize mixed effects regression modeling to estimate changes in serum creatinine (SCr) over the study period, accounting for baseline SCr and the correlation structure between the repeated measures. All potential confounders will be added to the model and sequentially removed if they do not confound the association between receipt of terlipressin and improvement in Scr. Those confounders resulting in a $\geq 10\%$ change in the coefficient for the association between terlipressin and improvement in SCr will be retained in the final model. For all generated models, Aikaike Information Criteria (AIC) scores will be calculated and compared. The model with the smallest absolute AIC value will be accepted as the most parsimonious and will be used as the primary model for the explanation of study results. As has been undertaken in other terlipressin studies in HRS, a least-squares means analysis will be conducted using a repeated-measures analysis of variance. The results from this approach to the statistical analysis can then be directly compared to prior study results.

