15.6 Safety Population

The safety population is defined as all subjects who received at least 1 dose of study drug.

16 Direct Access, Data Handling, and Record Keeping

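### Section 7.5 lets undefined significant deviations take a patient out of the Intent-To-Treat analysis, and Section 15 defines no efficacy set to override it

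*Combined protocol and SAP*

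**What the plan says.** Section 7.5 deals with departures from the protocol during conduct. Its reporting step begins "In the event of a significant deviation from the protocol due to an emergency, accident, or error": the investigator telephones the sponsor as early as possible. The purpose given is this: "This will allow an early joint decision regarding the subject's continuation in the study". The section then closes with "Significant deviations from the protocol may not allow that patient's clinical data to be included in the Intent-To-Treat Analysis".

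Section 15 does not take this up. Section 15.6 defines one analysis set: "The safety population is defined as all subjects who received at least 1 dose of study drug". Section 15.5 promises a summary of deviations but gives no exclusion rule and no sensitivity analysis. Apart from Section 7.5, intent-to-treat appears only in the abbreviation list.

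The control group has its own entry rules. Under Section 8.4 control treatment "will be recorded as noted in the patient's medical record", and "To be included as a completed subject in this study, patients must have been treated for at least 48 hours with albumin infusions"; vasopressors too must have been used for at least 48 hours. Section 7.2 also requires controls to meet the eligibility criteria, "as well as having critical clinical data points to enable a comparison of the Prospective and Retrospective groups".

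**The concern.** An intent-to-treat analysis keeps subjects whatever happens after entry. Section 7.5 keeps the name and permits the opposite, case by case and without criteria. Treatment is open-label and SCr, the primary outcome, is recorded every day. Unless the decision is tied to a fixed rule or date, it can be made by someone who has already seen the result.

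The rule also falls unevenly. The telephone report and the decision on continuation make sense only for an enrolled prospective subject. Controls were treated before the protocol applied to them, and their treatment is taken from the chart as given.

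Two results are exposed. One is the terlipressin group's own SCr change, the primary efficacy assessment in Sections 5.1 and 13.1. The other is the modelled "association between receipt of terlipressin and improvement in Scr" in Section 15.1, together with the secondary comparisons of dialysis and survival. A reader of the final report could not check an exclusion against any pre-specified rule.

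**Working it through.** **Inputs from the documents (Sections 15.2 and 15.3).** 50 terlipressin subjects and 150 controls; two-sided alpha 0.05; power 80%; detectable SCr differences of 0.46, 0.34 and 0.23 mg/dL at SDs of 1.00, 0.75 and 0.50 mg/dL.

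**Step 1: reproduce the stated figure.** Detectable difference = SD × (1.960 + 0.842) × √(1/150 + 1/50).
- At SD 1.00: 2.802 × 0.1633 = 0.457, stated as 0.46. A t-test version gives 0.460.
- At SD 0.75 and 0.50: 0.343 and 0.229, stated as 0.34 and 0.23.

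These three entries reproduce.

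**Step 2: assumptions.** The documents give no expected number of deviations and no outcome gap. Let k of the 50 treated subjects be dropped, and let their mean SCr change be worse than that of the retained subjects by g mg/dL. I take k = 2 to 5 and g = 0.5 to 1.5.

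**Step 3: shift in the mean.** If the retained mean is r, the full mean is [(50 − k)r + k(r + g)]/50 = r + kg/50. Dropping the k subjects therefore flatters the terlipressin mean by kg/50.

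| k | g (mg/dL) | Shift kg/50 (mg/dL) | Share of 0.46 |
|---|---|---|---|
| 2 | 0.5 | 0.02 | 4% |
| 2 | 1.0 | 0.04 | 9% |
| 5 | 0.5 | 0.05 | 11% |
| 3 | 1.5 | 0.09 | 20% |
| 5 | 1.0 | 0.10 | 22% |
| 5 | 1.5 | 0.15 | 33% |

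If the dropped subjects did better than the rest, g is negative and the shift goes against terlipressin.

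**Step 4: effect on the two-group test when there is no true difference.** Let SE = SD × √(1/150 + 1/(50 − k)) and b = kg/50. The rejection rate is Φ(−1.96 + b/SE) + Φ(−1.96 − b/SE).

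| k | g (mg/dL) | SD 1.00 | SD 0.75 | SD 0.50 |
|---|---|---|---|---|
| 0 | any | 5.0% | 5.0% | 5.0% |
| 2 | 1.0 | 5.7% | 6.2% | 7.7% |
| 5 | 0.5 | 6.0% | 6.8% | 9.1% |
| 5 | 1.0 | 9.1% | 12.3% | 21.8% |

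For example, with k = 5, g = 1.0 and SD 1.00, SE = √(1/150 + 1/45) = 0.170 and b/SE = 0.10/0.170 = 0.59.

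**Step 5: lost precision.** With 45 treated subjects the detectable difference at SD 1.00 is 2.802 × 0.170 = 0.476, and power at 0.46 falls from 80.4% to 77.2%. This cost is minor next to the possible bias.

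Steps 4 and 5 use a simple comparison of two means, not the planned mixed model, and assume no other source of bias between the groups.

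**The case against.** Four stronger readings are tempting, and the documents do not support them.

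- **That the events removed would be dose interruptions, early stops or a switch to another vasopressor, and so would track poor outcome.** The Synopsis provides for interruption, for stopping treatment, and for discontinuing terlipressin when another vasopressor is used; Section 8.4 repeats the interruption rule. None of these is a deviation as such. Section 7.5 concerns emergencies, accidents and errors. A preparation error need not relate to prognosis, and an eligibility error is fixed at baseline. An emergency deviation made to protect the subject is a more plausible marker of a poor course, but no figure in the documents confirms this.
- **That the sponsor and investigator remove subjects once outcomes are visible.** The early joint decision in Section 7.5 is about continuation. On who decides about the data, and when, the plan is silent. Silence permits an outcome-aware decision; it does not prescribe one.
- **That this is the only rule governing the efficacy data, so the comparison must favour terlipressin.** Controls pass through the 48-hour treatment and data-availability filters. The first can remove early control failures and so flatter the controls.
- **That the effect is necessarily large.** That needs adverse inputs throughout: a 1.5 mg/dL gap is 1.5 times the largest tabulated SD. Under milder inputs the false-positive rate at SD 1.00 is about 6%.

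It can also be said that the intent-to-treat label looks like template text, that the Synopsis plans descriptive analysis, and that deviations and all deaths are reported elsewhere (Sections 15.4 and 15.5). This limits how much could go unseen. It does not protect the efficacy estimates, and Section 15.2 does plan tests at P < 0.05. What remains is a written permission to exclude, without criteria, that nothing in Section 15 withdraws.

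**Conclusion.** The point holds as a defect in the definition of the analysis set. As written, the plan allows treated subjects to be left out of an analysis called intent-to-treat for a reason it does not define, at a time and by a decision-maker it does not name.

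That the rule acts on the terlipressin group alone is an inference from its reporting steps and from the controls having no study regimen; Section 7.5 does not say so. The direction favours terlipressin only if the excluded subjects did worse. The within-group SCr change is exposed with no counterweight. For the comparison with controls, the 48-hour filter makes the net bias unknown.

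The size rests wholly on assumed k and g: 0.02 to 0.15 mg/dL over the range shown, or 4% to 33% of the stated detectable difference at SD 1.00. It may be negligible in practice, but the plan contains nothing that would keep it so.

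**What to change.** Delete the last sentence of Section 7.5. In Section 7.5 and again in Section 15, state: *The primary and secondary efficacy analyses include all prospective subjects who received at least one dose of study drug and all controls who meet the control inclusion rules, regardless of protocol deviations. Subjects with significant deviations are excluded only in a labelled sensitivity analysis, under criteria fixed before outcomes are reviewed.* The one-dose rule is the definition already in Section 15.6. The list of significant deviations has to be written to go with it.

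The cost is a few sentences and that list; no treatment rule changes. For SCr on treatment, footnote f of Table 1 already asks for daily values to Day 14 or discharge whatever the treatment status. A subject not continued in the study after a deviation may still lack later data, so the plan should say that follow-up continues where the subject agrees and how gaps will be handled.

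The change does not remove the difference between a one-dose rule for treated subjects and a 48-hour rule for controls. That asymmetry should be acknowledged when the comparison is reported.

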8.1 Packaging and Labeling

Single-use, sterile 6-mL vials of a lyophilized solid containing 1 mg of terlipressin acetate (equivalent to 0.85 mg terlipressin free base) will be provided to the sites. Study drug labels will comply with local regulatory requirements, including sponsor name and address, protocol number, storage conditions and US Investigational New Drug (IND) caution statement.

8.2 Study Drug Storage and Preparation

Study drug should be stored in a secure location at 2°C to 8°C until reconstituted. Reconstituted study drug bolus and study drug infusion bags may be stored up to 48 hours at refrigerated storage conditions (2°C to 8°C) and at room temperature (25 °C) for 24 hours. (Appendices A and C).

Terlipressin is stable at 2°C to 8°C up to 48 hours in 0.9% sodium chloride solution at a concentration of 1mg Terlipressin in 5mL solution (Appendix A).

Microbiology studies at a concentration of 2 mg Terlipressin in 50 mL of 0.9% sodium chloride solution are included in Appendix C. Stability at a concentration of 0.034 mg/mL has been previously demonstrated (Bui 2020). Study drug assignment, preparation, and dosing will be strictly limited to the investigators and their designees. Study doses will be labelled to ensure drug is used only for authorized investigational use only. The subject's initials will be placed on the label by the Pharmacists at the time of dispensing.

8.3 Reconstitution

Collaborative Research Study, Version 4: 06/29/21
To Treat HRS-AKI Patients with Continuous Terlipressin Infusion

For the first dose of terlipressin, each vial will be reconstituted with 5 mL of sterile 0.9% sodium chloride solution and administered intravenously as a bolus injection and given over 1 minute at a dose of 0.5 mg.

For continuous infusion, the dose of terlipressin is to be dissolved in 0.9% sodium chloride solution and infused with a pump (Appendix B).

8.4 Administration

Subjects in the Prospective Terlipressin Group:

Single-use, sterile 6-mL vials containing 1 mg of lyophilized terlipressin acetate (equivalent to 0.85 mg terlipressin free base) with 10 mg mannitol as a bulking agent/stabilizer.

- For initial bolus dose of 0.5mg, the vial will be reconstituted with 5 mL of sterile 0.9% sodium chloride solution and given over 1-minute push.
- Continued dosing will be by 2mg infusion per day for Days 1, and 2. For continuous infusion, the dose of terlipressin is to be dissolved in 0.9% sodium chloride solution and infused with a pump.
- If on Day 3 the SCr is not 30% lower from the baseline value, increase infusion dose to 4 mg per day.
- If on Day 5 the SCr is not 50% lower from the baseline value, increase infusion dose to 6-8 mg per day, per PI discretion. Dosing can be increased by more than 1 mg increment at Day 5 or beyond, up to a maximum of 8 mg/day.
- If the subject has infusion stopped for \geq 4 hours, a 0.5 mg bolus should be given prior to restarting infusion.
- The drug should not be used in subjects with severe coronary artery disease or in the setting of circulatory overload, pulmonary edema, or bronchospasm as determined by the Investigator. If drug therapy has been initiated, Investigator can also decide not to increase the dose, based on the patient's status with regard to the above, based on individual subject condition.

- If dosing is interrupted due to an adverse event, terlipressin may be re-started, at the discretion of the investigator, at the same or lower dose as per protocol. Terlipressin will not be restarted if dosing was interrupted due to cardiac ischemia or mesenteric ischemia.

Subjects in the Retrospective Control Group:

The dose and method of administration for Midodrine/Octreotide (M&O), albumin, or other vasopressor will be recorded as noted in the patient's medical record. To be included as a completed subject in this study, patients must have been treated for at least 48 hours with albumin infusions beyond volume resuscitation and diuretic withdrawal. Vasopressors also need to be used for a minimum of 48 hours.

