Dosing for M&O, albumin, or other vasopressor will be reported as it was recorded on the subject's chart.

For Prospective Terlipressin Group:

Terlipressin will be supplied in single-use, sterile 6-mL vials containing 1 mg of lyophilized Terlipressin acetate (equivalent to 0.85 mg Terlipressin free base) with 10 mg mannitol as a bulking agent/stabilizer.

Initial Dosing:

Terlipressin will be administered intravenously as a bolus injection (the vial will be reconstituted with 5 mL of sterile 0.9% sodium chloride solution and given over 1 minute at a dose of 0.5 mg).

- Continued dosing will be by 2 mg infusion per day. For continuous infusion, the dose of terlipressin is to be dissolved in 0.9% sodium chloride solution and infused with a pump.

Dose Modifications:

- If on Day 3 the SCr is not 30% lower from the baseline value, increase infusion dose to 4 mg per day.
- If on Day 5 the SCr is not 50% lower from the baseline value, increase infusion dose to 6-8 mg per day, per PI discretion. Dosing can be increased by more than 1 mg increment at Day 5 or beyond, up to a maximum of 8 mg/day.
- If the subject has infusion stopped for \geq 4 hours, a 0.5 mg bolus should be given prior to restarting infusion.
- The drug should not be used in subjects with severe coronary artery disease or in the setting of circulatory overload, pulmonary edema, or bronchospasm as determined by the Investigator. If drug therapy has been initiated, Investigator can also decide not to increase the dose, based on the patient's status with regard to the above, based on individual subject condition.

Collaborative Research Study, Version 4: 06/29/21
To Treat HRS-AKI Patients with Continuous Terlipressin Infusion

- If dosing is interrupted due to an adverse event, terlipressin may be re-started, at the discretion of the investigator, at the same or lower dose as per protocol. Terlipressin will not be restarted if dosing was interrupted due to cardiac ischemia or mesenteric ischemia.

Treatment Discontinuation:

- Terlipressin may be continued until 24 hours after serum creatinine has reached the lowest value possible as determined by Principal Investigator, up to a maximum of 14 days.
- After a minimum of 72 hours post final dose escalation and tolerability, if the SCr is at or above enrollment value, terlipressin should be discontinued.

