7.3 Inclusion/Exclusion Criteria

Adult subjects with a diagnosis of HRS-AKI based on 2015 revised International Ascites Club (IAC) diagnostic criteria will be considered for enrollment. There are two groups: 1. listed for liver transplant or liver transplant eligible with anticipation of being placed on the liver transplant wait list; 2. Ineligible for liver transplant

Inclusion Criteria: Subjects must meet all of the following inclusion criteria to be eligible for enrollment:

1. Written informed consent by subject or legally authorized representative.
2. At least 18 years of age.
3. Cirrhosis and ascites.
4. No sustained improvement in renal function (less than 20% decrease in SCr) at least 48 hours after diuretic withdrawal and after plasma volume expansion with albumin (given daily for two days - 48 hours minimum from 1st dose). If SCr improves by $\geq 20\%$ but plateaus ($\leq 10\%$ fluctuation in sCr) and remains above 1.5 mg/dl for \geq another 48 hrs and there are no features of acute tubular necrosis.

Collaborative Research Study, Version 4: 06/29/21
To Treat HRS-AKI Patients with Continuous Terlipressin Infusion

5. Increase in SCr by at least ≥ 0.3 mg/dl OR 1.5-2 fold above baseline (AKI stage 1 and above), to a SCr of ≥ 1.5 mg/dl at the time of initiating treatment. Baseline SCr is defined as the most recent, lowest SCr within last 6 months before date of current admission.
6. A.) On liver transplant wait list or liver transplant eligible with anticipation of being placed on the liver transplant wait list. B.) Patients not on the transplant waitlist or transplant eligible are also eligible for the trial (maximum 25 subjects)

Exclusion Criteria: If any of the following exclusion criteria are met, the subject will not be enrolled:

1. Serum creatinine level greater than 5.0 mg/dL. Subjects with value greater than 5.0 mg/dL may be enrolled with Sponsor prior approval.
2. MELD score ≥ 35
3. Acute on Chronic Liver Failure (ACLF) grade 3 (according to the CLIF Consortium grading system).
4. Uncontrolled sepsis and/or uncontrolled bacterial infection (e.g., persisting bacteremia, persisting ascitic fluid leukocytosis, fever, increasing leukocytosis with vasomotor instability).
5. Shock.

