Record RRT, TIPS, transplant, and mortality ^j			Monitor and record throughout active study period and follow-up.																		
Record all paracentesis events			Record all paracentesis performed until drug treatment discontinued																		

Collaborative Research Study, Version 4: 06/29/21
To Treat HRS-AKI Patients with Continuous Terlipressin Infusion

All assessments are completed per Standard of Care.

^aMaximum treatment of 14 Days.

^bFemale subjects of child-bearing potential must have a negative urine or serum pregnancy test within 14 days prior to the first dose of study treatment.

^cThe qualifying SCr value (SCr value at least 48 hours after both diuretic withdrawal and the beginning of albumin fluid challenge) is considered the Enrollment SCr and must be drawn prior to start of study drug. The qualifying SCr value must be ≥ 1.5 mg/dL AND Baseline SCr is defined as the most recent, lowest SCr within last 6 months before date of current admission.

^dA general standard of care physical assessment of the major body systems evaluating any new clinically significant abnormalities within the following: general appearance, skin, head/eyes/ears/nose/throat, neck, heart, lungs, abdomen, extremities, and neurological systems. The investigator may perform additional unscheduled examinations to manage or evaluate a suspected AE as clinically necessary. The physical examination will also include weight and height.

^eCollection of the data from the last electrocardiogram done prior to admission and the electrocardiogram performed during admission, if performed as per standard of care

^fMust be performed at least once daily during active treatment AND until Day 14 (regardless of treatment status) or discharge, whichever occurs first. BUN & eGFR are recorded if taken per site standard of care. If assessments are performed more than once daily as part of the subject's medical care, all values are to be recorded on the CRF. If subject has SCr, BUN and/or eGFR, including Vital signs taken at any of the Follow-up Periods, they are to be recorded on the CRF.

^gSerious Adverse Events will be required to be collected only for the Prospective Terlipressin Group.

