10.2 Pre-Treatment Period

The pre-treatment period occurs prior to administration of study drug and includes performing baseline assessments and collection of prior medication information.

The qualifying SCr value (SCr value at least 48 hours after both diuretic withdrawal and after the beginning of albumin fluid challenge) is considered the enrollment SCr and must be drawn prior to study drug administration.

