10.3 Active Study Period (14 Days)

Dosing (Up to 14 Days)

The active study period extends from the initiation of study treatment through Day 14 or discharge from the hospital for any reason, whichever occurs first. Study drug will be administered as described in Section 7.3.2. Concomitant medications will be collected during this active study period. See Table 8.1 for the schedule of assessments during the active study period.

End of Treatment, Discharge or Day 14

Terlipressin may be continued until 24 hours after serum creatinine has reached the lowest value possible as determined by Principal Investigator, up to a maximum of 14 days.

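### The Day 3 and Day 5 dose-escalation tests use a creatinine reference that conflicts with the protocol's own definition of Baseline SCr

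*Combined protocol and SAP*

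**What the plan says.** Infusion starts at 2 mg/day. The Day 3 rule in 8.4 is "If on Day 3 the SCr is not 30% lower from the baseline value, increase infusion dose to 4 mg per day". The Day 5 rule is that if "on Day 5 the SCr is not 50% lower from the baseline value, increase infusion dose to 6-8 mg per day, per PI discretion". The Synopsis (Dose Modifications) has the same wording.

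Inclusion criterion 5 defines the term: "Baseline SCr is defined as the most recent, lowest SCr within last 6 months before date of current admission". Footnote c to Table 1, attached to the SCr row, repeats that definition. The same footnote gives the pre-dose qualifying value a different name: it "is considered the Enrollment SCr and must be drawn prior to start of study drug".

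The stopping rule in the Synopsis (Treatment Discontinuation) uses that second term. After at least 72 hours from the final escalation, "if the SCr is at or above enrollment value, terlipressin should be discontinued".

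Other sections use the word baseline for a time point just before treatment. Section 10.2 says that the pre-treatment period "occurs prior to administration of study drug and includes performing baseline assessments". The pretreatment column of Table 1 is headed as the baseline assessment and has a mark in the SCr row. Sections 12.2 and 13.1 have SCr taken at baseline and then daily.

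**The concern.** The reference value decides the dose of a vasoconstrictor, and the dosing bullets do not say which of two quantities it is. A site that looks up the defined term will use the lowest recent value before admission. A site that follows the assessment schedule will use the pre-dose value. Inclusion 5 requires SCr to have risen above the pre-admission value, so the two quantities differ in every eligible patient and the pre-admission value is always the lower.

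If sites differ, the treated group of about 50 subjects at 5 to 10 sites would mix two titration schemes. On the pre-admission reading, a patient whose kidney function has fully returned would still meet both triggers. Section 3.2 gives a lower total dose as one reason for using continuous infusion, so unintended escalation would work against the protocol's own rationale.

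**Working it through.** The plan gives no figure to reproduce on this point. The check is a comparison of definitions plus arithmetic.

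**Inputs**
- b = pre-admission Baseline SCr (inclusion 5; Table 1 footnote c).
- c = Enrollment SCr (Table 1 footnote c; section 10.2). Entry requires c of at least 1.5 mg/dL and a rise over b of at least 0.3 mg/dL or 1.5-2 fold.
- r = c/b, which is above 1 for every eligible patient.
- Thresholds of 30% (Day 3) and 50% (Day 5) from 8.4. I take the trigger to be a fall smaller than the stated percentage.

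**SCr at or below which the dose is not increased**
- Enrollment reading: 0.70c on Day 3, 0.50c on Day 5.
- Defined (pre-admission) reading: 0.70b on Day 3, 0.50b on Day 5.

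As a fall from Enrollment SCr, the defined reading requires 1 - 0.70/r on Day 3 and 1 - 0.50/r on Day 5. The enrollment reading requires 30% and 50% whatever r is.

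| r | Example b to c (mg/dL) | Day 3, defined reading | Day 5, defined reading |
|---|---|---|---|
| 1.25 | 1.2 to 1.5 | 44.0% | 60.0% |
| 1.5 | 1.0 to 1.5 | 53.3% | 66.7% |
| 2.0 | 1.0 to 2.0 | 65.0% | 75.0% |
| 3.0 | 1.0 to 3.0 | 76.7% | 83.3% |

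**One patient, two doses.** Take b = 1.0, c = 2.0 and a Day 3 SCr of 1.3.
- From Enrollment SCr: (2.0 - 1.3)/2.0 = 35% fall. This is at least 30%, so the dose stays at 2 mg/day.
- From Baseline SCr: (1.0 - 1.3)/1.0 = -30%, that is, 30% above the reference. The dose goes to 4 mg/day.

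For this patient the readings disagree for any Day 3 SCr above 0.7 (0.70 × 1.0) and up to 1.4 (0.70 × 2.0), and for any Day 5 SCr above 0.5 and up to 1.0.

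**Full return to the pre-admission value (SCr = b)**
- Defined reading: (b - b)/b = 0% for any b, so both triggers are met. This follows directly from the definition and is not an estimate of frequency.
- Enrollment reading: the fall is 1 - 1/r. It passes Day 3 if r is at least 1/0.70 = 1.43, and Day 5 if r is at least 1/0.50 = 2.0. For 1.0 to 2.0 and back to 1.0, the fall is 50% and both tests pass. For 1.2 to 1.5 and back to 1.2, it is 0.3/1.5 = 20% and both tests fail on either reading.

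**The case against.** The strongest reply is that the pre-dose value is plainly meant. The bullets do not use the defined label Baseline SCr. Table 1, 12.2 and 13.1 treat baseline creatinine as a pre-treatment sample. The Synopsis retreatment rule describes partial response as at least a 50% reduction during the first course, the same percentage as the Day 5 test, and a reduction during treatment is naturally counted from its start. A treating hepatologist is also unlikely to demand an SCr of 0.7 and then 0.5 mg/dL from a patient whose best recent value was 1.0. Most of this stands: the pre-dose value was probably intended. It does not remove the conflict. The contrary definition sits in a footnote on the very SCr row of Table 1, and the stopping rule beside the escalation rules names the enrollment value where they do not.

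A reader might infer that sites will escalate recovered patients, or that the protocol obliges them to. The documents do not support that. Under 7.4, "The investigator may discontinue any subject at any time for any reason". Section 10.3 adds an exit at the lowest SCr: "Terlipressin may be continued until 24 hours after serum creatinine has reached the lowest value possible as determined by Principal Investigator". Day 5 carries investigator discretion, although that may cover only the choice between 6 and 8 mg. These clauses let a site stop treatment; they do not tell it which reference to use.

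A reader might also infer that the percentage-fall rule is itself wrong, because a fully recovered patient with r below 1.43 fails Day 3 even from Enrollment SCr. That is a design choice and not an error. Full return after about 48 hours at 2 mg/day may be uncommon, and escalation can be defensible when the pre-admission SCr is above the 1.5 mg/dL reversal value in 3.3. What remains is narrow. The written option not to increase the dose is tied to the listed cardiac, fluid-overload and airway conditions, although its closing reference to the individual subject could be read more broadly. Holding at 2 mg/day on Day 3 because SCr has recovered is therefore not clearly provided for.

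**Conclusion.** The point holds as a conflict of terms with a dosing consequence. Read by the protocol's only definition, the escalation tests are anchored to the pre-admission low; read by the assessment schedule, they are anchored to a pre-dose sample. At r = 2.0 the fall from Enrollment SCr needed to avoid escalation is 30% on one reading and 65% on the other for Day 3, and 50% against 75% for Day 5.

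The arithmetic needs only the two definitions and the entry criteria; the patient values are illustrative. The protocol gives no distribution of r and no dose-specific rates of serious adverse events, so neither the share of patients affected nor the harm can be estimated. Nothing shows that any site has used or would use the pre-admission value. Confidence is high that the terms conflict, and no claim is made beyond that. Severity: minor.

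**What to change.** In the Day 3 and Day 5 bullets of both 8.4 and the Synopsis, replace the reference to baseline with: the Enrollment SCr (the qualifying value; if SCr was repeated before the first dose, the last value before study drug). The parenthesis is needed because Table 1 schedules SCr at both screening and the baseline assessment, and no maximum interval is set between the qualifying draw and the first dose. If one reference is wanted throughout, the 72-hour stopping rule can carry the same words.

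Optional, and not part of the error: add a permissive sentence that the investigator may hold the current dose at Day 3 if SCr has returned to the pre-admission Baseline SCr. It should not forbid escalation, which must stay open where SCr is still high. Its downside is that some patients with a high pre-admission SCr may stay on a lower dose at the investigator's choice.

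The cost is one wording amendment in two places. Pre-admission, enrollment and daily SCr are already collected, so no patients, visits, blood draws or CRF fields are added.
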